#### **2.1.2.5 MORTALITY RATES**

Information regarding mortality will be obtained from the 12-month combined notes review question “*Is the participant alive?*” (Variable *ISALIVE*), the SAE report (Variable *SAESER*), the HES database, the ONS database, and the SystmOne report. This outcome will be derived as a binary variable and will be coded as affirmative if there is evidence of death on any of the sources listed above, this outcome will be coded as negative if there is no evidence of death on any of these sources. If there is a contradiction between the sources the participant will be assumed to have died. If a participant had withdrawn consent to note review/follow-up and there is no evidence of a death prior to withdrawal, then this outcome will be missing.

#### **2.1.2.6 MRSA INFECTION/COLONISATION**

Whether or not a participant acquired a MRSA infection up to 12 months after randomisation will be obtained from the notes review at 12 months (Variable *MRSAYN*), as well as the SystmOne report.

#### **2.1.2.7 CLOSTRIDIODES DIFFICILE INFECTION**

Whether or not a participant contracted a *Clostridioides difficile* infection up to 12 months after randomisation will be obtained from the notes review at 12 months (Variable *CLSTDMYN*), as well as the SystmOne report.

#### **2.1.2.8 DE-LABELLING AT 3 MONTHS POST RANDOMISATION**

The proportion of ALABAMA participants whose labels are removed from the primary care medical electronic health record allergy section at 3 months post randomisation. This will be derived as affirmative if the participant was de-labelled on the de-labelling CRF (Variable *DELABELLEDYN*) and this occurred within 3 months (90 days) from randomisation (Variable *DELABELDAT*). Otherwise, this outcome will be negative. Participants who were not de-labelled within 3 months and withdrew consent for notes reviews to be conducted will have this outcome as missing.

#### **2.1.2.9 DE-LABELLING AT 12 MONTHS POST RANDOMISATION**

The number and proportion of ALABAMA participants whose labels were removed (delabelled) by 3 months post randomisation and the number/proportion of ALABAMA participants who were delabelled the primary care medical electronic health record up to 12 months post-randomisation. This outcome will be derived similar to the outcome above and will be classed as affirmative if the participant was de-labelled within 12 months (365 days) and were not relabelled (Variable *RELABELLED*). Separately, the number of trial participants who were relabelled after being delabelled, in each arm will be reported.

## **2.2 TARGET POPULATION**

Participants who were over 18 with a record of a penicillin allergy.

### **2.2.1 INCLUSION CRITERIA**

- Participant was willing and able to give informed consent for participant in the trial,
- Male or Female, aged 18 years or above,
- Current penicillin allergy (or sensitivity) record of any kind in their primary care electronic health record,
- Prescribed systemic antibiotics, either: penicillin, cephalosporin, tetracycline, quinolone macrolide, glycopeptide, aminoglycoside, oxazolidinone, monobactam, or carbapenem class antibiotic, or fosfomycin, nitrofurantoin, trimethoprim, clindamycin, rifampicin, colistin, metronidazole in the previous 24 months.

N.B.1 Patients who had been formally tested for penicillin allergy in the past and were found not to be penicillin allergic but still has a medical record indicating a penicillin allergy, were eligible for the trial.

### **2.2.2 EXCLUSION CRITERIA**

The participant may not enter the trial if ANY of the following applied:

- Life expectancy estimated <1 year by GP,
- Unable to attend hospital clinic where allergy testing takes place,
- Unsuitable for entry into testing pathway because:
  - Allergy history consistent with anaphylaxis to penicillin,

- History of toxic epidermal necrolysis, Stevens-Johnson syndrome, drug reaction with eosinophilia and systemic symptoms (DRESS) or any severe rash which blistered or needed hospital treatment, and acute generalised exanthematous pustulosis precipitated by a penicillin,
- Has been formally tested for penicillin allergy in the past and been found to be penicillin allergic,
- History of brittle/severe asthma or has had a course of steroids in the past 3 months for asthma or unstable coronary artery disease, or other severe/poorly controlled skin conditions,
- Or considered unsuitable for trial participation by the GP e.g. because of chaotic lifestyle.
- Pregnant,
- Breastfeeding mothers,
- Currently taking beta blocker medication, and unable to temporarily withhold these on the day of penicillin allergy testing,
- Currently taking (or recently taken) systemic steroids and unable to stop these for 10 days pre-testing,
- Or currently taking antihistamines and unable to temporarily withhold these for 72 hours pre-texting.

GPs may have also wanted to exclude vulnerable patients who were deemed to be unsuitable to participate for other reasons such as, but not limited to, terminal illness, reliability, mental illness, learning difficulties, anxiety, other family circumstances.

N.B.1 Patients that were currently taking medicines with antihistamine properties that cannot be temporarily withheld or patients with isolated dermographism may still have be eligible to participate but this needed to be discussed with the research team prior to consent.

N.B.2 Pregnancy and breastfeeding exclusion criteria was only applicable at screening (due to potential risks of PAT); these patients would not need to be withdrawn if in follow up.

## 2.3 SAMPLE SIZE

The primary outcome was initially treatment response failure defined as the percentage of re-prescription of an alternative antimicrobial within 28 days of an index prescription. A total sample size between 1592 and 2090 participants provided 80-90% power to detect a clinically important absolute difference of 7.9% in re-prescription rate at one year between groups (i.e. reducing from 19.8% in the control group to 11.9% in the PAAP group) at 5% level of significance (2-sided). The sample size had been adjusted assuming 50% of participants will require at least one prescription within 1 year from randomisation and allowing for 10% dropout. Participants are classed as enrolled at the point of randomisation.

The primary outcome was then changed to 'effects of PAAP on penicillin prescribing', defined as 'The proportion of participants who receive prescriptions for a penicillin attending for predefined conditions where a penicillin is the first-line recommended antibiotic (see Appendix II) during the course of routine primary care up to 12 months post randomisation. A total sample of 848 (i.e. 424 per group) was required to provide 90% power to detect an increase in the proportion of penicillin prescription from 4% (Usual Care) to 14% (PAAP) over the year after randomisation at 5% level of significance (2-sided) and 10% attrition. The sample size has been adjusted assuming 50% of participants will require at least one prescription within 1 year from randomisation. At 80% power, the sample size required was 656 (i.e. 328 per group). The table below also provides the sample size required if not all participants have reached 12 months follow-up.

Power	% Difference	Total sample size (all reached 12 months FU)	Total sample size (80% reached 12 months FU)	Total sample size (90% reached 12 months FU)
80%	10%	656	820	729
	15%	372	465	413
90%	10%	848	1060	942
	15%	472	590	524

Results from our recent analysis, using data extracted from the SystmOne database, suggested that there were an average of 110 patients per average practice size of 6000 who fulfilled our inclusion criteria.

- 1) Adults (over 18 years),
- 2) Penicillin allergy in electronic health records,
- 3) And in receipt of a penicillin, cephalosporin, tetracycline, quinolone, or macrolide class antimicrobial in the previous 24 months.

Not all patients will have an eligible antibiotic prescription for an infective episode during the follow-up period, and not all episodes will generate analysable data. We have allowed for 50% patients not contributing any data to the primary outcome.

## 2.4 RANDOMISATION AND BLINDING IN THE ANALYSIS STAGE

During their call with the research team, participants were asked if they had taken any antibiotics in the previous two weeks; if they had, the randomisation/baseline call was postponed until the participant was free of antibiotic use for two weeks. The research team arranged another call to take place when the participant had been free of antibiotic use for two weeks. During the call, the participants were asked to complete the baseline assessment and the member of the research team performed randomisation. Randomisation was performed using Sortition (PC-CTU's in-house online randomisation system) according to the current version of the SOP PC-CTU\_SOP\_IT104. Allocation was minimised by general practice, age, number of antibiotic prescriptions up to 24 months prior to randomisation, and number of Quality Outcome Framework registered diseases, to ensure balance of allocation of these baseline covariates. Patients were randomised to either usual care (with subsequent monitoring for antibiotic prescriptions and follow-up for trial outcomes as determined by the clinical indication for antibiotics) or the PAAP intervention arm using an allocation ratio of 1:1. Both the participants and the recruiter knew which arm they were randomised into. The trial statistician will remain blinded to treatment allocation when performing the final analysis. Unblinding of the allocation will take place in accordance with SOP PC-CTU\_SOP\_ST105.

N.B. Patients randomised to the PAAP trial arm, who do not attend an appointment for PAT, will continue to be followed up unless consent is withdrawn.

**NOTE:** There have been some errors made during the randomisation procedure, at least one participant's minimisation data has been entered incorrectly onto Sortition (and cannot be corrected). As such, the information collected on the baseline CRF (data from OpenClinica) will be used as covariates in the analysis regardless of the information that was used for the randomisation. Information from both the baseline CRF and the information used in the randomisation (Sortition) will be presented in the baseline table.

## **3 ANALYSIS – GENERAL CONSIDERATIONS**

### **3.1 DESCRIPTIVE STATISTICS**

Frequencies (with percentages) for binary and categorical variables, and means (with standard deviations), or medians (with lower and upper quartiles), and the range (minimum and maximum values) for continuous variables will be presented by randomised arm.

### **3.2 CHARACTERISTICS OF PARTICIPANTS**

The following baseline characteristics of participants from the baseline questionnaire and the baseline TPP form will be presented by randomised arm and overall (also see dummy table in Appendix V):

- Age (means and standard deviations, randomisation categories (from Sortition), and according to SOP ST101\_v4.0 (based on EudraCT guidelines) as adults 18-64 years, adults 65-84 years and adults 85 years and over),
- Gender,
- Ethnicity (collected from the notes review CRF),
- Index of multiple deprivation quintiles (IMD) (will be derived from a list of postcodes provided by the trial manager),
- Number of antibiotic prescriptions in the 24 months prior to recruitment (from both Sortition and TPP) (12 months for those recruited to the nested pilot study)
- Number of QOF registered diseased (from both Sortition and TPP)
- Other information from SystmOne (Antibiotic prescriptions in the 12 months prior to recruitment, and 12-24 months prior to recruitment, and number of participants with each each QOF registered disease).
- Patient reported penicillin allergy history (how long has the participant been allergic to penicillin, the name of the penicillin that cause the allergic reaction, how was the penicillin that caused the allergic reaction taken, allergic symptoms, how long after taking penicillin did the participant get the allergic reactions, did the participant consult a doctor or attend an emergency department, was the participant admitted to hospital, does the participant have an allergic reaction to another group of antibiotics)
- Patient reported other significant medical history (does the participant have any other medical conditions, pregnant or breast feeding, currently taking any antihistamines, taken steroids within the last 10 days, taking any other medication either prescribed by GP or bought over the counter),

There will be no tests of statistical significance nor confidence intervals for differences between randomised groups on any baseline variables reported.

Participant throughput from screening through randomisation, follow-up, and analysis will be presented in a flow diagram, and include reasons for withdrawal (see Appendix VI).

### **3.3 DEFINITION OF POPULATION FOR ANALYSIS**

The primary analysis population will include all randomised patients in the treatment arm they were assigned to, regardless of treatment received. All data will be included in the analysis as far as possible, though there will inevitably be the problem of missing data due to withdrawal, loss to follow-up, or non-response to questionnaire items.

Participants withdrawn for post-randomisation ineligibility will be excluded from the analyses. Those randomised but who were not eligible at the PAAP clinic will not be included in the analysis population. Those who were eligible but decided not to go ahead with PAAP will be included in the analysis population.

The primary analysis will also be carried out on the “as treated” (AT) analysis population. All participants who were allocated to PAAP and had exposure to the test (i.e., they completed either the skin test or oral challenge test, or both), will be included in the as-treated PAAP arm. Those participants who were randomised to PAAP but did not have a test or who were randomised to usual care will be included in the usual care arm.

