## **2 TRIAL DESIGN**

This is a multicentre, two parallel-arm, open label, individually randomised pragmatic trial with a nested pilot trial.

Potential participants who met the eligibility criteria were identified during a search of their electronic health records at their general practice. The electronic search criteria were developed centrally by the research team in partnership with TPP and made available for running locally on SystmOne e.g. by practice managers, Local Clinical Research Network (LCRN) Research Nurse Team, or Leeds CCG Pharmacy Technician team. Potential participants were sent an invitation pack and those interested in taking part returned an expression of interest form to the trial team. They were telephoned and booked into an either a face to face, or telephone appointment with their GP or Research Nurse at a time that was convenient to them. During this appointment, their GP or a delegated member of the staff confirmed their eligibility to participate and consented them to take part in the trial. The participants then received another telephone call from a member of the trial team to complete the baseline case report form (CRF). At this point, the participants were asked if they had taken any antibiotics in the previous two weeks; if they had, the randomised/baseline call will be postponed until the participant has been free of antibiotic use for two weeks.

Once the baseline CRF was complete the participants were randomised to usual care or the PAAP intervention arm. Those randomised to the PAAP intervention arm were booked into an appointment at the clinic where they had penicillin allergy testing.

Participants recruited during the nested pilot phase were followed up for an initial 4 months for the feasibility outcomes, during which they were contacted monthly by the trial team. Following a “stop go” assessment, all nested pilot study participants were subsequently followed up for at least 12 months in the main trial to align their follow-up with participants recruited to the main trial.

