### **2.1.1 PRIMARY OUTCOME – EFFECTS OF PAAP ON PENICILLIN PRESCRIBING**

The primary outcome is the effect of PAAP on penicillin prescribing, and is defined as: the proportion of participants who receive prescriptions for a penicillin when attending for predefined conditions where a penicillin is the first-line recommended antibiotic (see Appendix II) up to 12 months post-randomisation.

The primary outcome will be coded as 1 (“Yes”) if there is evidence of a penicillin prescription during the course of routine care, up to 12 months post randomisation on any of the following data sources: SystmOne report/notes review (Variable *ISPRIMARYEVENT*), patient follow-up calls, or hospital prescribing reports. Participants that have not required penicillin treatment during the trial will have their primary outcome coded as 0 (“No”).

Participants who do not have evidence of a prescription and who withdrew consent for notes review to be conducted, will have their primary outcome missing at 12 months.

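### Section 3.3 drops patients found ineligible at the PAAP clinic, which only the PAAP arm attends after open-label randomisation, so the primary analysis set is filtered in one arm

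*SAP*

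**What the plan says.** SAP section 3.3 opens with the intention-to-treat principle: "The primary analysis population will include all randomised patients in the treatment arm they were assigned to, regardless of treatment received". Two exclusions follow. The first is general: "Participants withdrawn for post-randomisation ineligibility will be excluded from the analyses". The second is specific to the clinic: "Those randomised but who were not eligible at the PAAP clinic will not be included in the analysis population". The same paragraph then keeps another group of untested patients: "Those who were eligible but decided not to go ahead with PAAP will be included in the analysis population".

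On who reaches the clinic, section 2 says: "Those randomised to the PAAP intervention arm were booked into an appointment at the clinic where they had penicillin allergy testing". Section 2.4 describes usual care only as monitoring for antibiotic prescriptions and outcome follow-up, and says of the allocation: "Both the participants and the recruiter knew which arm they were randomised into".

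Section 6.1 repeats that the primary analysis keeps participants in their randomly assigned arm whether or not they received the intervention.

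**The concern.** Clinic eligibility is judged after randomisation, and in one arm only. A PAAP patient with a disqualifying feature found at the clinic leaves the analysis. A usual-care patient with the same feature is never seen there and stays in. The SAP describes no equivalent check for usual care, though the protocol, which is not shown, may do so.

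The rule also conflicts with the first sentence of 3.3 and with 6.1. Being untested cannot be its justification, because eligible patients who decline testing are kept.

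What is at stake is the primary relative risk. If the excluded patients have a lower chance of a penicillin prescription than the PAAP patients kept, the planned estimate is too high. If their chance is higher, it is too low. With no true effect, the expected estimate moves away from 1 in either direction.

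**Working it through.** **Do the later analyses repair it?**

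| Section | What it does | Restores clinic-ineligible patients to the PAAP arm? |
|---|---|---|
| 6.1 | Regroups by test received; a PAAP patient without a test counts as usual care | No |
| 6.2 | Adds predictors of missingness to the model | No |
| 6.3 | Removes patients without 12 months of follow-up | No |
| 6.4 | Removes patients tested more than 90 days late | No |

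**Inputs.** From section 2.3: 4% (usual care) against 14% (PAAP), 50% of participants needing a prescription, 424 per group, 10% attrition. Section 2.1.1 codes participants who needed no penicillin as 0, so the rates among all randomised are 0.5 × 4% = 2% and 0.5 × 14% = 7%. The share excluded, *f*, is not in the SAP; 2%, 5% and 10% are assumed (about 8, 21 and 42 of 424).

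**Plan's own figure.** The continuity-corrected two-proportion formula for 4% against 14% at 90% power gives 190 per arm. Then 190/(0.5 × 0.9) = 422.2, rounded up to 423 per arm, or 846 in total against the stated 848. The inputs are therefore read as the SAP meant them. The sample size itself is not in question.

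**Shift in the relative risk.** Take the RR in the retained set as 7%/2% = 3.50. With *x* the risk in the excluded patients, the RR in all randomised is [(1 − f) × 7% + f × x]/2%. For example, f = 5% and x = 2% give (6.65% + 0.10%)/2% = 3.375, and 3.50/3.375 = 1.037.

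| Excluded share | x = 2% (usual-care rate): all-randomised RR | Planned RR too high by | x = 0: planned RR too high by | x = 14% (double): planned RR too low by |
|---|---|---|---|---|
| 2% | 3.45 | 1.4% | 2.0% | 2.0% |
| 5% | 3.38 | 3.7% | 5.3% | 4.8% |
| 10% | 3.25 | 7.7% | 11.1% | 9.1% |

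If 3.50 is instead taken as the RR in all randomised, the one-sided exclusion with x = 2% gives 3.55, 3.63 and 3.78, which is the same picture.

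**Against the precision of the trial.** SE(log RR), unadjusted, is √[(1 − 0.07)/(n₁ × 0.07) + (1 − 0.02)/(n₀ × 0.02)], with n₀ = 424 × 0.9 = 381.6 and n₁ = n₀(1 − f). This gives 0.405, 0.406 and 0.409. The shift in log RR, divided by the SE, is 0.04, 0.09 and 0.18 for x = 2%, and 0.05, 0.13 and 0.26 for x = 0.

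**No true effect.** If the excluded have *k* times the risk of the others, the expected RR is 1/[(1 − f) + f × k].

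| Excluded share | k = 0.5 | k = 2 |
|---|---|---|
| 5% | 1.03 | 0.95 |
| 10% | 1.05 | 0.91 |

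Rejection of a true null at the nominal two-sided 5% level (normal approximation, common rate 2% to 7%):

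| Excluded share | k = 0 (extreme) | k = 0.5 |
|---|---|---|
| 5% | 5.1% to 5.4% | 5.0% to 5.1% |
| 10% | 5.5% to 6.9% | 5.1% to 5.4% |

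**The case against.** The strongest reply is about size. Eligibility is confirmed before randomisation, and the baseline call asks about allergy history, antihistamines and recent steroids (sections 2 and 3.2). Pregnancy or breastfeeding after screening does not require withdrawal (2.2.2). Few patients should then fail at the clinic, and nothing in the SAP supports a share as high as 10%. Even there the shift is at most about a quarter of a standard error. This stands, and it limits the severity. It does not justify the rule, because the SAP gives no count that would show the exclusions to be few.

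A second reply is that the general sentence on post-randomisation ineligibility is worded for both arms, so usual-care patients can be removed too. The wording does allow that. But the SAP describes no usual-care procedure that would find such patients, and the clinic sentence has no usual-care counterpart.

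Third, excluding ineligible patients can be legitimate. It can, where ineligibility rests on facts recorded before randomisation and is judged in the same way in both arms, blind to allocation. Section 3.3 sets none of these conditions.

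Finally, knowledge of the allocation adds little by itself. The imbalance comes from who attends the clinic, and nothing shows that knowing the arm changes the check.

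**Conclusion.** The concern holds. As written, section 3.3 filters the PAAP arm on a post-randomisation finding that usual care cannot have, against the SAP's own stated principle, and no planned analysis undoes this. It is a flaw of validity that should be corrected, probably of small size. Over assumed exclusions of 2% to 10%, the relative risk is overstated by between 1.4% and 11.1%, or understated by between 2.0% and 9.1%, depending on the prescribing risk of the excluded patients. Both that risk and the excluded share are assumptions, so neither the size nor the direction can be fixed from the SAP. The conclusion about one-sidedness rests on the SAP alone and would soften if the protocol describes an equivalent check in usual care.

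**What to change.** In section 3.3, remove the clinic-ineligibility exclusion from the primary analysis, and amend the sentence before it so that it cannot take out the same patients. Possible wording:

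> Participants found not eligible for testing at the PAAP clinic remain in the PAAP arm as untested participants. A participant is excluded only if records made before randomisation show ineligibility, assessed identically in both arms and blind to allocation.

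Also:

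- Derive the outcome of these patients by the rule in 2.1.1. It is missing only for "Participants who do not have evidence of a prescription and who withdrew consent for notes review to be conducted", and otherwise 0 or 1.
- Keep the present analysis set as a labelled sensitivity analysis in section 6.
- State that in the as-treated analyses they count as usual care, which already follows from the definition in 3.3 for PAAP patients without a test.
- Show exclusions by arm and reason in the diagram that section 3.2 already plans: "Participant throughput from screening through randomisation, follow-up, and analysis will be presented in a flow diagram, and include reasons for withdrawal".

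The cost is SAP wording and outcome derivation for the restored patients. Section 2 says that all trial participants had case note review, which suggests that the data largely exist, but the SAP does not confirm it for patients withdrawn as ineligible. A few more PAAP-arm outcomes may be missing. The exception for pre-randomisation ineligibility is optional; if used, it needs a blinded review of records. The sample size is unaffected, and the estimate may move either way.

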## 5 SECONDARY ANALYSIS

### 5.1 BINARY OUTCOMES

The binary secondary outcomes:

- Treatment “response failure”,
- Hospital admission,
- Mortality rates,
- MRSA infection/colonisation,
- *Clostridioides difficile* infection,
- De-labelling at 3 months post randomisation (to be analysed in the as treated population),
- And de-labelling up to 12 months post randomisation (to be analysed in the as treated population)

will be analysed using a binomial mixed-effects generalised linear model with a logit link function. The models will include randomised group (as treated group for the de-labelling outcomes), age, number of antibiotic prescriptions in the 24 months prior to randomisation (12 months for those recruited to the nested pilot study), and the number of QOF registered diseases as fixed effects. GP practice will be included as a random effect. The adjusted relative risk between the randomised groups and the corresponding 95% confidence intervals will be obtained from the marginal adjusted relative risk between the randomised groups and reported alongside the associated P-value.

If it is possible that the de-labelling outcomes could unblind the report, the summary statistics will not be presented in the blinded report, only the treatment effects will. In this case, the summaries will only be presented in the unblinded report, once the blinded report is signed off. If there is insufficient data to compare the treatment groups, no formal analysis will be carried out and only summary statistics will be presented.

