## **6.4 EXCLUDING PARTICIPANTS WHO HAD DELAYED PAAP**

There may be cases where a participant who was randomised to PAAP did not receive PAAP for quite some time. The primary analysis (section 4.1) will be re-run with the participants who were delayed in receiving the PAAP by more than 3 months (90 days) excluded from the analysis population.

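### For 3-month de-labelling, a PAAP participant first tested after day 90 counts as a treated non-event, while one never tested, in the same position at day 90, counts as usual care

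*SAP*

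**What the plan says.** Four parts of the SAP bear on this outcome.

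- **Group (section 3.3).** The as-treated PAAP arm is "All participants who were allocated to PAAP and had exposure to the test", meaning a skin test, an oral challenge or both. The as-treated usual care arm takes "Those participants who were randomised to PAAP but did not have a test or who were randomised to usual care". Neither definition mentions the date of the test.
- **Analysis (section 5.1).** The list of binary outcomes includes "De-labelling at 3 months post randomisation (to be analysed in the as treated population", and the as-treated group replaces the randomised group in the model. No comparison by randomised arm is planned for this outcome.
- **Outcome (section 2.1.2.8).** De-labelling is positive if "this occurred within 3 months (90 days) from randomisation". For everyone else, "Otherwise, this outcome will be negative", apart from those not de-labelled in the window who withdrew consent to notes review; they are missing.
- **Late testing (section 6.4).** The SAP foresees it: "There may be cases where a participant who was randomised to PAAP did not receive PAAP for quite some time". Its response is to re-run the primary analysis with participants "delayed in receiving the PAAP by more than 3 months (90 days) excluded from the analysis population". The opening of section 6 confines sensitivity analyses to the primary outcome. It points to a section 6.6 for exceptions, but the text has no such section.

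**The concern.** Group membership can be settled by an event that happens after the outcome window has closed. A test on day 120 can neither cause nor prevent a label being removed by day 90, yet it decides which arm the participant's day-90 result is counted in.

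The as-treated comparison is the only one planned for 3-month de-labelling, and a reader will take it as showing what happens to people who were tested. With late-tested participants in the treated arm, the figure mixes two things: labels not removed after a timely test, and tests that had not yet taken place. The re-run in section 6.4 does not separate them, because it does not extend to this outcome.

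**Working it through.** **Step 1. Apply the rules to two participants.** Both are randomised to PAAP, and both are untested and still labelled at day 90.

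| | Participant A | Participant B |
|---|---|---|
| First test | day 120 | never |
| Label removed | day 135 | never |
| State at day 90 | untested, labelled | untested, labelled |
| 3-month outcome (2.1.2.8) | No | No |
| As-treated arm (3.3) | PAAP | usual care |

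A cannot fall in the usual care arm, because that arm admits only PAAP participants who had no test. The two differ only in what happened after day 90.

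**Step 2. Inputs for the size.** The SAP states no figure for late testing or for de-labelling, so there is nothing of its own to reproduce. All three inputs are assumptions:

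- f: share of tested participants first tested after day 90;
- p: 3-month de-labelling among those tested by day 90;
- p0: de-labelling by day 90 without a test, taken to apply to the late-tested as well.

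**Step 3. Formula.** The as-treated PAAP proportion is a mixture:

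observed = (1 − f)p + f·p0

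The shortfall against p is therefore f(p − p0). It is positive whenever f > 0 and p > p0, and zero when f = 0.

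**Step 4. Numbers with p0 = 0.**

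| p | f = 0 | f = 5% | f = 10% | f = 20% | f = 30% |
|---|---|---|---|---|---|
| 50% | 50.0% | 47.5% | 45.0% | 40.0% | 35.0% |
| 70% | 70.0% | 66.5% | 63.0% | 56.0% | 49.0% |
| 90% | 90.0% | 85.5% | 81.0% | 72.0% | 63.0% |

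For example, 0.95 × 70% = 66.5% and 0.80 × 70% = 56.0%. For f from 5% to 30% the shortfall runs from 0.05 × 50 = 2.5 points to 0.30 × 90 = 27 points.

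**Step 5. Some de-labelling without a test.** p0 need not be zero, since section 2.2.1 admits people who had already tested negative but whose record still carries the label. With p = 70%, p0 = 2% and the comparator held at 2%:

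- f = 0: relative risk 70 / 2 = 35.0;
- f = 10%: observed 0.90 × 70% + 0.10 × 2% = 63.2%, relative risk 31.6;
- f = 20%: observed 0.80 × 70% + 0.20 × 2% = 56.4%, relative risk 28.2.

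At f = 20% the relative risk falls by 1 − 28.2/35.0 = 19.4%, slightly less than f.

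**The case against.** The strongest reply is that the outcome is timed from randomisation, not from testing. A label still in place at day 90 is correctly coded No, and waiting for the clinic is arguably part of a pathway that section 1.3 presents as streamlined. The coding is indeed right. But counting delay against the pathway calls for an analysis by randomised arm. The as-treated rule moves the never-tested out of PAAP and keeps the late-tested in, so it measures neither the pathway as a policy nor what follows a test.

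Several other points stand and limit the finding:

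- The size is unknown and may be nil. Section 6.4 says only that such cases may exist.
- The understatement is relative to participants tested in the window. Against an analysis by randomised arm, the as-treated proportion could still be higher, because untested PAAP participants have been removed from it.
- Under the assumptions in Step 5, a very large relative risk stays very large, so no change of qualitative conclusion is shown.
- Late removals are not lost. Participant A counts as Yes at 12 months unless relabelled.

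A reader might infer three stronger things that the document does not support. One is that the 12-month outcome and the as-treated run of the primary outcome are distorted in the same way. That would need first tests after day 365, and nothing suggests any. Another is that clinic delay will be read as GPs failing to act on results; the SAP attributes delay to nobody. The third is that the relative risk is understated by exactly f. That holds only if no late-tested participant is de-labelled by day 90.

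**Conclusion.** The point holds for 3-month de-labelling. It is a defect in a stated rule rather than a missing detail: sections 3.3 and 5.1 sort participants by a test at any time, while section 2.1.2.8 closes the outcome at day 90. The direction follows from the definitions if anyone was first tested after day 90 and timely testing raises de-labelling. The size is f(p − p0). On the assumed p = 70% and p0 = 0, that is 3.5 points at f = 5% and 14 points at f = 20%. These values are illustrations, since the SAP supplies none of the three inputs. The primary outcome analysis by randomised group and the sample size are not touched. The rule should be corrected, because this is the only planned comparison for a named secondary outcome and the SAP itself anticipates the delay.

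**What to change.** In sections 3.3 and 5.1:

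1. State that, for 3-month de-labelling, the as-treated PAAP group requires a first test on or before day 90 from randomisation.
2. State where PAAP participants first tested later go in the two-group model. Excluding them matches the rule in section 6.4. That section does not spell out where its 90 days begin, so name randomisation as the start here.
3. Report descriptively how many were tested after day 90 and how many of them were de-labelled.

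This takes two or three sentences and no new data, because test dates and randomisation dates are already needed for section 6.4. The costs are a smaller treated group and a further selection on a post-randomisation event, in a comparison that is already non-randomised. Some waiting time also remains in the figure: a participant tested on day 88 has only two days in which to be de-labelled. The descriptive report would let readers judge how much the exclusion matters.
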